5.0 Risks

Possible risks from the study include administration of radiopharmaceuticals and oral d-amphetamine, venipuncture, and the discomforts associated with PET scanning

Radiopharmaceuticals: Subjects are exposed to radiation from the two [¹⁸F]fallypride scans and, the single [¹⁸F]FE-PE2I scan, and the CT scans that are used for attenuation correction. The total radiation dose associated with one PET study is approximately 1900 mrem. This dose corresponds to the background radiation received in 6 years from the environment. Dosing at this level is within FDA guidelines, and large-scale studies of the long-term risk of radiation exposure (within FDA limits) have shown no increase in rates of cancer associated with this amount of exposure.

In addition, there is a potential adverse response to the injections themselves. This risk is minimal because [¹⁸F]fallypride and [¹⁸F]FE-PE2I are injected at subpharmaceutical (tracer-level) doses, and procedures are in place to ensure quality control in terms of requirements for high specific activity, chemical purity and demonstrated sterility. [name] and colleagues have now performed over 200 [¹⁸F]fallypride PET studies at Vanderbilt and have seen no laboratory abnormalities from administration of this radiopharmaceutical. The only adverse event seen in these studies was a single subject who became nauseous, but review of the case suggested that this may have related from hypoglycemia due to fasting before the study.

We lack past experience with injecting [¹⁸F]FE-PE2I at Vanderbilt, but no reports of adverse events have been reported at other institutions using the radioligand, and qualifying runs have shown suitable specific activity, chemical purity and sterility. A nuclear medicine physician will be available within the Department of Radiology in case a problem arises that requires attention.

Administration of Amphetamine: The primary risks associated with the use of dAMPH include an increase in blood pressure, psychological effects (i.e. feeling jittery, anxiety, increased alertness and restlessness), and difficulty sleeping. Numerous studies of oral dAMPH in normal volunteers have been reported. A 0.5 mg/kg oral dose of dAMPH produced a mean elevation of 28 mm Hg increase in systolic blood pressure at 2 hours, i.e. a peak systolic blood pressure of 148 which decreased to a 14 mm Hg increase at 4 hours and returned to normal levels by 6 hours. The pulse rate remained unchanged [145,176]. Our own data in young adults exposed to our standard dose of 0.43 mg/kg indicates a mean increase of approximately 27 mm HG at peak (148 mm Hg) that occurs by 3 hours, and decreases substantially by completion of scanning. Based on these data we anticipate that a 0.43 mg/kg dose of dAMPH should produce blood pressure elevations of 25-30 mm Hg on average. To limit risk, we apply strict blood pressure restrictions on enrollment (systolic no more than 150 mm Hg). The average systolic blood pressure is 120 (average range: 108-133) for the age range 20-30, and 130 (average range: 116-144) for the age range 50-60. With an inclusion cutoff of 150 mm Hg, we do not anticipate many participants exceeding 180 mm Hg on dAMPH. This is within the normal range for systolic blood pressure for exercise (160 - 220 mm Hg). Participants with a reported history of labile hypertension will also be excluded, since they would be at increased risk for a blood pressure elevation. Participants will also be given an EKG and will be excluded if there are any abnormalities that would represent a risk under a condition of temporary elevation of blood pressure. Participants' blood pressure will be monitored by medical staff during their time in the study (every half hour), and standard of care intervention will be administered if there is a sustained elevation in blood pressure > 200 mm Hg

for more than 30 minutes. The default treatment strategy for sustained high blood pressure will be administration of 0.3 mg oral clonidine, which typically begins lowering blood pressure within 30 minutes. We note that in the unlikely event that the study physician felt a more rapid lowering of blood pressure was essential for patient safety, the study MD could select administration of intravenous nitroprusside as part of a standard of care treatment for a blood pressure emergency, but we do not anticipate any situations in which this should be necessary. We note it in the protocol only for purposes of thoroughness – and any case where this would be necessary would warrant an adverse event report to the IRB. In all of our past studies intervention has never been necessary following amphetamine (although we note that the majority of subjects studied in our lab to date were under 40 years of age). A study medical doctor ([name] or his surrogate) will be in the PET suite or the medical campus throughout all procedures and will be notified immediately if blood pressure exceeds 170 mm Hg systolic on any reading.

Psychological effects range from positive effects to some mild negative subjective emotional states including feeling jittery, anxious or restless. These negative emotional states resolve within a few hours of drug administration and are consistently gone by the time subject's leave the study. Participants are given a number to reach the investigators if they are experiencing any acute negative emotional events in the hours after they leave the study, although we have never had a participant feel the need to contact us following exposure to amphetamine. Participants may have difficulty falling asleep in the evening after amphetamine administration. They are advised of this, and told: 1) not to make any major decisions or drive following the study, and 2) not to schedule anything too early in the morning the next day. The study staff will make transportation arrangements in cases where someone does not have a ride option after the scans. We additionally try to start drug administration by 2 PM in the afternoon, so that 8-hours have passed by a typical bedtime.

There is a potential ethical concern regarding the administration of psychostimulant drugs to healthy non-drug using normal control subjects. We have relied on guidelines developed by the National Advisory Council on Drug Abuse (NACDA; appointed by the Secretary of Health and Human Services and Advisory to the National Institute of Drug Abuse). The entire report is available at: <http://www.nida.nih.gov/funding/hsguide.html>. In addition, we have relied on the "Human Subject Issues in Drug Abuse Research" published by the College on Problems of Drug Dependence (Adler, 1994) which states "There is no evidence that exposure to drugs in a research setting enhances the desire of an individual to use drugs, leads the individual to addiction, worsens the addiction of an individual, or makes an addict more difficult to treat". For the sake of thoroughness, we have provided pertinent excerpts from the most recent NACDA guidelines as a supplement to this application.

Venipuncture: There is a risk of local bruising and discomfort associated with venipuncture for obtaining blood samples and placement of IV lines for the PET studies. A small amount of bleeding may occur when an IV line is inserted or removed. While there is the possibility of infection associated with venipuncture, this is very unlikely. Participants with anemia are excluded in order to avoid problems associated with repeated blood draws.

Discomfort associated with PET scanning: Participants may experience some discomfort due to having to remain motionless for up to 70 minutes at a time during PET scanning. Participants are given pillows to help them get comfortable before the start of the scans.

5.1 Reporting of Adverse Events or Unanticipated Problems Involving Risk to Participants or Others

Each study will be monitored by [name] or one of the approved study M.D.'s in his absence. The physician will monitor vital signs, physical and mental status, in real-time, to assess for adverse events and safety concerns. Subjects will be discharged with instructions to call immediately for any concerning signs or symptoms. Adverse events will be classified mild, moderate or severe as follows:

- 1) Mild – Adverse effects including events which do not produce functional impairment and do not require intervention or promptly respond to treatment.
- 2) Moderate – Moderate side effects include events and pharmacological effects which may affect function and pharmacological effects of drugs which do not respond promptly to treatment but are reversible over a period of hours.
- 3) Severe - Adverse effects are those which are life-threatening, incapacitate the subject, and in the case of pharmacological effects do not respond to treatment and do not resolve within hours.

Adverse events or unanticipated events will be attributed to the study as follows:

- 1) Probable: The adverse event is likely related to the study.
- 2) Possible: The adverse event occurs within 96 hours of the end of the study, but may be related to other factors.
- 3) Unrelated: The event occurs more than 96 hours after the end of the study and is more likely due to extraneous factors. Probable or possible serious adverse events will be reported to the IRB within 10 days.

All potentially serious adverse events will be reviewed on a real time basis. All adverse events will be reviewed with [name] during regular review meetings. Any adverse events that could be deemed moderate or greater, and probable or possible, will lead to a meeting with [name] at his earliest possible schedule opening (within 48 hours of the event). All events that either the PI or [name] consider to be severe adverse events, which are probably or possibly related to the study will be reported within 7 days to the IRB, and within 10 days to the FDA by [name] (and [name], who is the physician in charge of the institutional IND), and NIA program officer by ([name]). Additionally, any unanticipated event that is considered moderate and possibly or probably related to the protocol will be reported to the IRB (but not the FDA or NIDA program officer) within 10 days. Annual reports of all adverse events (regardless of severity) will be made to the IRB (by [name]) and FDA (by [name] and [name]). Note, non-pharmacological adverse events, such as vasovagal responses to the placement of the IV line, will not be included as part of FDA reporting as they are unrelated to the investigational drug.

Data and Safety Monitoring

The PI will meet with the data safety monitor on an annual basis to review participant data. Data to be reviewed will include any descriptions of impaired functioning reported by the medical staff involved in the project including pre- and post-administration neurological exam, pre- and post-administration vital sign, CBC and CMP. Any unanticipated adverse events will be reviewed with the data safety monitor within 48 hours of the event in order to evaluate the event, determine reporting requirements, and evaluate if protocol changes are necessary.

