 - k) Diabetes, hypoglycemia, or any condition that could would prevent the participant from fasting for 6 hours
 - l) Recent participation in studies involving radiation or routine occupational exposure to radiation.
 - m) High blood pressure (Systolic B.P. > 150), or an abnormal EKG indicating potential cardiac risk under conditions of increased blood pressure. If subject is over 60, baseline B.P. > 145.

Inclusion/Exclusion criteria are determined based on data obtained during IRB#141812 (with the exception of the plasma pregnancy exam for women of child-bearing potential which is collected within 48 hours prior to each PET scan. At any point in the study, the study PI ([name]), or one of the study physicians may withdraw a participant if they find new evidence that the participant has an exclusionary condition.

Up to 70 subjects may be consented for the study, with the aim of having 60 subjects total complete the PET studies. No more than 60 subjects (30 per age group, with equal gender representation). No subjects will be consented after the 60th participant is scheduled for a PET scan unless we have another withdrawal from the study.

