4.0 Study Procedures

4.1 Primary Study Procedures: The study involves 4 sessions: Informed Consent, Fallypride PET + placebo, Fallypride PET + oral d-amphetamine, and PE2I PET. The 3 PET sessions will be conducted within a 6 week window, and whenever possible within a 2 week time period.

4.2. Informed consent session: Informed consent will be obtained by [name] or approved study personnel after inclusion and exclusion criteria have been reviewed. This will be done in the Dept. of Psychology at Vanderbilt University. Written consent materials are provided to the participant originally when they complete the related IRB protocol #141812. Although given to participants during Part I of the study, Participants only sign the consent for the 2nd part of the study after completing the prior study and passing inclusion and exclusion criteria assessed during that study.

In the present study, participants are given time to read (or reread) the written informed consent document in a quiet private room. They are asked if they have any questions about the protocol. If they have no questions or the researcher has any concerns about whether they understand the procedures, the researcher will briefly review the steps of the study. Because the participants will have already completed IRB #141812, the researchers will already have some knowledge of the participants level of cognitive functioning, and if there is a concern about the participants ability to understand the procedures based on their past performance on cognitive measures they will be excluded from the study.

After the potential participant indicates they have read the document, [name] or his associate will briefly review specific procedures and their risks (especially those related to administration of amphetamine and PET radioisotopes), and the subject will be given a chance to ask questions. The participants will only be asked to sign the informed consent document after any and all questions have been answered.

After signing the informed consent, participants will receive a brief training on how to perform the two-stage task (this will help reduce the amount of time needed for training on that task on the fallypride PET scan days). Participants will also complete the Tests of Vigilance and Attention (TOVA: <http://www.tovatest.com/>), which assesses attention abilities and motor impulsivity.

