4.3 Specific procedures for female subjects of child-bearing potential: Premenopausal without hysterectomy or similar procedure, will need to have an additional blood draw within 48 hours prior to each PET session to rule out pregnancy (blood drawers will typically be scheduled within 36 hours preceding the planned time of radioisotope administration). Women who are premenopausal will be only studied within the first 10 days of their menstrual cycle.

4.4 Fallypride PET Sessions (with placebo or oral d-amphetamine).

Participants complete two [¹⁸F]fallypride PET sessions, each lasting approximately 7 hours. Scan sessions will all start in the afternoon. Subjects will be instructed to have a moderate lunch with no more than a single cup of coffee or tea before coming to the PET center. If the scan is not expected to start until after 5 PM, a light snack may also be eaten. After determination of blood pressure, respirations, pulse, temperature, an intravenous line will be placed in the forearm, the subject will complete ratings of their mood (using the and PANAS and the Amphetamine Interview Schedule administered on a laptop computer), and participants will have a brief neurological exam conducted by one of the study MDs. An initial blood sample for genotyping or estradiol levels (women only) will be acquired.

The subject will then receive a 0.43 mg/kg oral dose of d-amphetamine or placebo. The investigational pharmacy will prepare capsules with 10 mg, and 2.5 mg with dosing rounded to the nearest 2.5 mgs (for instance an individual weighing 80 kg would be rounded up to a 35 mg dose). The drug dose and placebo, will be placed by the pharmacist in identical containers, labeled with the subject's ID and scan day number. A sealed envelope indicating whether the dose is d-amphetamine or placebo will be included in case there is a need to break the blinding. The study physician, can quickly access this information if there is appearance of an adverse drug effect. Otherwise the study physician and experimenters who have contact with the participant will remain blind until the participant has completed their second PET scan. If a participant has an adverse event that necessitates any medication, or other intervention, the blind will be broken to the participant.

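### The systolic limit in 3.2(m) is applied to Part I data and is not made a condition of giving the capsule, although blood pressure is read just before each dose

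*Combined protocol and SAP*

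**What the plan says.** **The limit.** Section 3.2(m) excludes "High blood pressure (Systolic B.P. > 150), or an abnormal EKG indicating potential cardiac risk under conditions of increased blood pressure". It adds "If subject is over 60, baseline B.P. > 145". Section 5.0 describes the 150 limit as one placed on enrollment: "To limit risk, we apply strict blood pressure restrictions on enrollment (systolic no more than 150 mm Hg".

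**When it is assessed.** Section 3.2 states "Inclusion/Exclusion criteria are determined based on data obtained during IRB#141812". The one exception named is the plasma pregnancy test, done within 48 hours before each PET scan. The PI or "one of the study physicians may withdraw a participant if they find new evidence that the participant has an exclusionary condition".

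**Dosing day.** Section 4.4 opens each fallypride session with a reading: "After determination of blood pressure, respirations, pulse, temperature, an intravenous line will be placed in the forearm". Mood ratings and a brief neurological exam by a study MD follow, and then the capsule. No blood pressure value is named as a condition for giving it.

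**Numeric triggers elsewhere.**
- Above 170 on any reading, the study physician is notified (5.0).
- Above 180, readings are taken every 15 minutes (4.4).
- Above 200 for more than 30 minutes, clonidine may be given (4.4, 5.0).

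**Expected effect.** Section 5.0 anticipates an average rise of 25 to 30 mm Hg. Given the 150 cutoff, it does not expect many participants above 180.

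**The concern.** The safety argument in 5.0 adds a rise to a starting pressure, and the start that matters is the one when the drug is taken. The plan fixes that start at an earlier study and gives no maximum interval between the Part I reading and the dose. A participant who passed in Part I and reads 158 on the day can be dosed without any departure from the written procedure.

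The dose is oral, and the investigators' own data put the peak by 3 hours. The half-hourly readings after dosing can therefore detect a rise but not prevent it. Participants are healthy volunteers. The older group has the higher average pressure (130 against 120), and 5.0 itself notes that most past amphetamine subjects in this laboratory were under 40.

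**Working it through.** **1. The plan's own figure.** Cutoff plus mean rise: 150 + 25 = 175 and 150 + 30 = 180. This matches the 180 in 5.0. At the over-60 limit it is 145 + 25 to 30 = 170 to 175.

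**2. The same sum from a start above the limit.**

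| Pre-dose systolic | Mean projected peak | Action the plan requires before dosing |
|---|---|---|
| 151 | 176 to 181 | none stated |
| 155 | 180 to 185 | none stated |
| 160 | 185 to 190 | none stated |
| 170 | 195 to 200 | none stated |
| above 170 | above 195 | physician notified; no hold stated |

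For those over 60 the uncovered range starts at 146, unless 'baseline' in item (m) means the session reading. The document does not say.

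**3. How often a dosing-day reading exceeds the limit.** The document gives no SD, so this is an assumption with a range. Older mean 130 and range 116 to 144 are from 5.0, where they describe ages 50 to 60; I apply them to the whole older group. If the range is ±1 SD, SD = 14/1 = 14. If it is ±1.96 SD, SD = 14/1.96 = 7.1. Let w be the visit-to-visit SD (5 to 10 assumed; 5 to 7 for the smaller SD). Readings are taken as normal with correlation 1 − w²/SD² between visits. The count is 30 × P(pre-dose > c | Part I ≤ 150).

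| SD, w | c = 150 | c = 155 | c = 160 | c = 170 |
|---|---|---|---|---|
| 14, 5 | 0.93 | 0.25 | 0.04 | 0.00 |
| 14, 7 | 1.29 | 0.47 | 0.14 | 0.01 |
| 14, 10 | 1.78 | 0.79 | 0.31 | 0.03 |
| 7.1, 5 to 7 | 0.07 to 0.08 | 0.01 | 0.00 | 0.00 |

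At least one of the two fallypride days above 150: about 1.5 to 3.2 of 30 with SD 14, and about 0.15 with SD 7.1. In the young group (mean 120, SD 12.5 or 6.4) the count is 0 to 0.2 of 30 per day and 0 to 0.5 over two days. At the 145 limit, with the same mean of 130, 1.5% to 10.4% of those who passed would read above it on a given day. The number over 60 is not stated.

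**4. What a hold would prevent.** Take the SD 14 case and assume a rise with mean 27.5 and SD 8 to 15. Of 30 older participants, about 1.4 to 3.7 would peak above 180 without a hold. About 0.9 to 2.7 would still do so from starts at or below 150. Roughly 45% to 85% of such peaks therefore remain. Peaks above 200 fall by about 0.01 to 0.26 of 30, before the 30-minute duration condition is applied.

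**The case against.** The best case against is that the plan does not leave dosing unguarded. Section 5.0 excludes reported labile hypertension, the history most relevant to someone who passes once and reads high later, and it excludes EKG findings that would be a risk under raised pressure. A study MD examines the participant between the reading and the capsule (4.4). A physician monitors vital signs in real time (5.1). Withdrawal on new evidence of an exclusionary condition is allowed throughout (3.2). A competent physician might well hold the dose at 160. Further, 180 is not a harm threshold in this plan: 5.0 places it within the exercise range, and treatment starts only above a sustained 200.

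Much of this stands. A reader might infer that nothing protects a participant whose pressure is high on the day, or that many would be dosed above the limit. The documents support neither. The safeguards are real, and the labile-hypertension exclusion makes the upper end of the frequency range in the working probably too high.

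What does not stand is that these measures amount to the limit. The labile-hypertension exclusion depends on reported history. The withdrawal clause is permissive and concerns leaving the study; it does not say when to repeat a reading, hold a dose or reschedule. Section 6.0 is also permissive, and its reason on exclusion criteria covers findings during screening. Different physicians may cover sessions, so judgement may vary. The plan does set such conditions elsewhere: pregnancy testing is tied to each scan, and release after scanning requires normal vital signs.

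**Conclusion.** The concern holds in a limited form. As written, the procedure permits a pressor dose when the pre-dose systolic is above the limit on which 5.0 rests its 180 expectation. No reading is named at which the dose is held. The gap does not end at 170, because that trigger only notifies. This conclusion comes from the text and is firm.

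The size is small and uncertain. About 0.1 to 1.8 of 30 older participants per dosing day would read above 150, probably toward the lower end, and at most 0.03 above 170. These figures depend on normality, on how the undefined 116 to 144 range is read, and on an assumed visit-to-visit SD. How Part I measured blood pressure is not in this document. It would be wrong to conclude that the 180 expectation fails: it says only that not many will exceed 180, and that may be right. Nor would a hold secure it, since on the assumed SDs about 45% to 85% of peaks above 180 would remain. The point merits correction because the plan's timing rule undercuts its own safety premise, and a reading already taken can repair it.

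**What to change.** Add to 4.4: on both fallypride days the pre-dose systolic, repeated after rest if high, must meet the 3.2(m) limits before the capsule is given; otherwise the session is rescheduled. Apply it on both days, because the staff present are blind to which day carries drug. The study physicians should set the rest interval and number of repeats. State also whether 'baseline' for those over 60 means the session reading.

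**Cost.** No new measurement is needed beyond an occasional repeat. On the assumptions above, a first reading over 150 on at least one of the two days affects about 0.1 to 3.2 of 30 older and 0 to 0.5 of 30 young participants. The 145 limit adds some, and repeat readings release some. Both fallypride scans are needed for the change in binding, so a participant who cannot be rescheduled loses that measure from a sample planned at 30 per group.

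Scheduling is tightest for premenopausal women: "Women who are premenopausal will be only studied within the first 10 days of their menstrual cycle", while "The 3 PET sessions will be conducted within a 6 week window, and whenever possible within a 2 week time period". On an assumed 28-day cycle, one postponement spans at most day 1 to day 38, or 37 days, which fits 6 × 7 = 42. A second postponement after a completed scan spans at least day 10 to day 57, or 47 days, which does not.

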6.0 Study Withdrawal/Discontinuation

Subjects may elect to withdraw from the study at any point. The investigator may discontinue an individual's participation in the study for the following reasons:

- 1) The participant becomes pregnant.
- 2) The subject is found during screening to have laboratory results, physical findings, or psychiatric history that are exclusion criteria.
- 3) The subject has an adverse events of moderate severity or greater who, in the judgment of the principle investigator, may be unable to complete the study or whose health may be compromised by further participation. If an adverse event occurs, immediate treatment will be provided.
- 4) A subject cannot complete the study in a reasonable period of time, i.e. >3 months. Subjects will be informed of this possibility orally and then in writing prior to discontinuation.

If a subject is discontinued by the investigator during the initial session of the study or because of a failed drug screen, they will not be reimbursed for their time. If they are discontinued because of medical or psychiatric reasons, they will be compensated at a rate of \$10 per hour spent in the study up to a total of \$150. If the study was discontinued after administration of [¹⁸F]fallypride, the subjects will be paid for the complete study.

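### The severity scale mixes severity with response to treatment, so a life-threatening drug effect that is treated successfully falls, on the literal wording, outside the grade that triggers expedited FDA reporting

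*Combined protocol and SAP*

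**What the plan says.** Section 5.1 of the combined protocol and SAP sets three grades, and each refers to response to treatment.

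- *Mild* includes "events which do not produce functional impairment and do not require intervention or promptly respond to treatment".
- *Moderate* covers effects that may affect function, and "pharmacological effects of drugs which do not respond promptly to treatment but are reversible over a period of hours".
- *Severe* effects are those that are "life-threatening, incapacitate the subject, and in the case of pharmacological effects do not respond to treatment and do not resolve within hours".

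The same section ties actions to the grade. It is enough that the PI or a second named reviewer judges an event severe and at least possibly related. Such an event "will be reported within 7 days to the IRB, and within 10 days to the FDA"; the funder's program officer is also told. Related events that could be moderate or worse lead to a review meeting within 48 hours. Section 6.0 uses the grade too: one reason for discontinuation begins "The subject has an adverse events of moderate severity or greater".

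Section 5.0 (Administration of Amphetamine) describes oral medication as the default for sustained high blood pressure and an intravenous drug as a further option. Of the intravenous option it says that "any case where this would be necessary would warrant an adverse event report to the IRB". It says nothing similar of the oral default.

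**The concern.** Severity describes how bad the event was for the participant. Response to treatment describes what happened afterwards. If the grade depends on the second, successful treatment lowers the recorded severity of the event itself.

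This matters here because the hazard the protocol plans for is acute, pharmacological and treatable. Section 5.0 expects mean systolic rises of 25 to 30 mm Hg on d-amphetamine. It notes that most people previously studied in this laboratory were under 40, whereas 30 of the planned 60 completers are in the older group. At stake are prompt notice to the FDA and the program officer, the 7-day IRB report, the 48-hour review meeting, and the link from grade to discontinuation.

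**Working it through.** No arithmetic decides this point. The check sets the grades beside the reporting routes.

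**Step 1: the ladder for drug effects.** Taken together, the definitions run from prompt response (mild, if function is unimpaired), through slow but reversible response (moderate), to no response and no resolution within hours (severe). The severe definition joins its parts with *and*. Reversible drug effects already have a place under moderate, which supports reading the severe conditions as cumulative. A drug effect that either responds to treatment or resolves within hours then fails the severe definition, however dangerous it was.

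**Step 2: the mild definition.** I read it as no functional impairment, together with either no need for intervention or prompt response. This is the more favourable reading. The sentence could also be parsed so that prompt response alone is enough for mild.

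**Step 3: a test case from Section 5.0.** Systolic pressure stays above 200 mm Hg beyond half an hour, the oral default is given, and the participant responds promptly with function unimpaired. On the literal wording the event is mild. The routes then stand as follows.

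| Route | Condition | Reached by the written scale? |
|---|---|---|
| IRB 7 days, FDA 10 days, program officer | Severe and related | No; only if a reviewer considers it severe |
| 48-hour review meeting | Could be moderate or worse, and related | Not if mild |
| IRB 10 days | Moderate, unanticipated, related | Not if mild; a blood pressure rise is also a listed primary risk |
| IRB 10 days, and real-time review of potentially serious events | Serious | Possibly; the term is not defined |
| IRB report, no deadline | Intravenous drug needed | No; oral drug used |
| Data safety monitor, 48 hours | Unanticipated | Arguable |
| Annual report to IRB and FDA | Any adverse event | Yes |

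**Step 4: the same case, life-threatening but reversed by treatment.** The cumulative severe definition still fails. The event is moderate if it may have affected function or was slow to respond, and otherwise mild. The serious route to the IRB becomes much more likely, but that route does not mention the FDA. The only expedited FDA route runs through the severe grade.

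**Step 5: the other reading of severe.** If the conditions are alternatives, a life-threatening event is severe and the first route applies in full. But a drug effect then also becomes severe merely by not responding and not resolving within hours. Difficulty sleeping is a listed primary risk; if it lasted the night it could qualify for expedited FDA reporting. Neither reading gives a workable scale.

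**Step 6: consistency elsewhere.** Section 4.4 unblinds the participant when an adverse event requires medication or another intervention. Section 5.1 can grade that same event mild.

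**The case against.** A reader might infer that a treated life-threatening reaction can never be graded severe and escapes expedited reporting altogether. The documents do not support that.

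- The severe sentence is ambiguous and can be read as a list of alternatives.
- The trigger is a judgement: either of two reviewers may consider an event severe.
- Probable or possible serious events go to the IRB within 10 days whatever their grade, and potentially serious events are reviewed in real time. A life-threatening reaction would be hard to exclude from serious, even undefined.
- An emergency plausibly may affect function, which would make it at least moderate. The 48-hour meeting has a low threshold.
- Intravenous rescue is described as not anticipated. An event needing it could therefore count as unanticipated, with data safety monitor review within 48 hours.

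A reader might also infer that the Section 5.0 statement on intravenous rescue contradicts the scale. It does not: it adds an IRB report whatever the grade.

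The scenario is also expected to be uncommon. A participant at the 150 mm Hg entry limit with the expected mean rise reaches 150 + 25 = 175 to 150 + 30 = 180 mm Hg, below the 200 mm Hg treatment threshold. The limit is 145 for those over 60, and the protocol reports that intervention after amphetamine has never been needed.

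All of this stands, and it limits the point mainly to the FDA, program-officer and 7-day IRB reports. It does not remove it. Reviewer judgement is meant to apply the written scale, and that scale points away from severe. The main IRB backstop depends on an undefined term.

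**Conclusion.** Wrong as written. On the literal wording, *severe* excludes a life-threatening or incapacitating drug effect that responds to treatment or resolves within hours. *Mild* can include an event that needed intervention. For such events the expedited FDA and program-officer reports and the 7-day IRB report rest on a reviewer's judgement against the scale. Expedited IRB reporting is not necessarily lost, because the serious route may apply, but with a 10-day deadline instead of 7.

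The conclusion assumes the cumulative reading of the severe definition, which the wording and the moderate grade favour without settling. On the alternative reading the under-reporting disappears and over-reporting of minor lasting effects takes its place, so rewording is needed either way. The documents give neither an event rate nor the spread of the blood pressure response, so the number of events affected cannot be stated. It may be zero.

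**What to change.** Amend Section 5.1 as follows.

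1. Grade all three levels on the participant's state at the worst point of the event. Remove response to treatment from mild, moderate and severe together. Deleting it from mild alone would leave minor, promptly treated events without a grade and keep the same fault in moderate.
2. State that life-threatening and incapacitating are each sufficient for severe.
3. Define serious separately from severe, and reconcile its 10-day IRB deadline with the 7 days for severe events. Say whether related serious events also go to the FDA and the program officer on an expedited timetable.
4. Reconcile Sections 4.4, 5.0 and 5.1 on how events that need medication are graded and reported, covering oral as well as intravenous treatment, and give the Section 5.0 report a deadline.
5. Check that the Section 6.0 discontinuation criterion still means what is intended once the grades change.

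The cost is a wording amendment and possibly a few more reports. Sample size, study procedures and analyses are unaffected.
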